**7. ACUTE-PHASE REACTANT VALUE**

A westergren erythrocyte sedimentation rate (ESR) or a C-reactive protein (CRP) level will be assessed.

## APPENDIX H: TUBERCULIN SKIN TESTING

An intradermal tuberculin skin test (Mantoux) must be performed within 1 month prior to the first administration of study drug following the instructions provided below. Multiple puncture tests (Tine and Heaf) are not acceptable methods of testing.

### Administering the Mantoux Tuberculin Skin Test

The Mantoux tuberculin skin test (CDC, 2000) is the standard method of identifying persons infected with *Mycobacterium tuberculosis*. Multiple puncture tests should not be used to determine whether a person is infected. Multiple puncture tests are not reliable because the amount of tuberculin injected intradermally cannot be precisely controlled. Tuberculin skin testing is both safe and reliable throughout the course of pregnancy. The Mantoux tuberculin test is performed by placing an intradermal injection of 0.1 mL of tuberculin into the inner surface of the forearm. The test must be performed with tuberculin that has at least the same strength as either 5 tuberculin units (TU) of standard purified protein derivative (PPD)-S or 2 TU of PPD-RT 23, Statens Serum Institut, as recommended by the World Health Organization. PPD strengths of 1 TU or 250 TU are not acceptable (Menzies, 2000). Using a disposable tuberculin syringe with the needle bevel facing upward, the injection should be made just beneath the surface of the skin. This should produce a discrete, pale elevation of the skin (a wheal) 6 mm to 10 mm in diameter. To prevent needle stick injuries, needles should not be recapped, purposely bent or broken, removed from disposable syringes, or otherwise manipulated by hand. After they are used, disposable needles and syringes should be placed in puncture-resistant containers for disposal. Institutional guidelines regarding universal precautions for infection control (eg, the use of gloves) should be followed. A trained health care worker, preferably the investigator, should read the reaction to the Mantoux test 48 to 72 hours after the injection. Patients should never be allowed to read their own tuberculin skin test results. If a patient fails to show up for the scheduled reading, a positive reaction may still be measurable up to 1 week after testing. However, if a patient who fails to return within 72 hours has a negative test, tuberculin testing should be repeated. The area of induration (palpable raised hardened area) around the site of injection is the reaction to tuberculin. For standardization, the diameter of the induration should be measured transversely (perpendicular) to the long axis of the forearm. Erythema (redness) should not be measured. All reactions should be recorded in millimeters, even those classified as negative.

### Interpreting the Tuberculin Skin Test Results

In the US and many other countries, the most conservative definition of positivity for the tuberculin skin test is reserved for immunocompromised patients, and this definition is to be applied here, even though the patients entering this study may or may not be immunocompromised at baseline. The purpose of using this conservative definition of positivity is to maximize the likelihood of detecting latent TB. In the US and Canada, an induration of 5 mm or greater in response to the intradermal tuberculin skin test is considered to be a positive result and evidence for either latent or active TB.

In countries outside the United States and Canada, country-specific guidelines for **immunocompromised patients** should be consulted for the interpretation of tuberculin skin test results. If no local guidelines for immunocompromised patients exist, US guidelines must be followed.

### Treatment of Latent Tuberculosis

Local country guidelines for immunocompromised patients should be consulted for acceptable antituberculous treatment regimens for latent TB. If no local guidelines for immunocompromised patients exist, US guidelines must be followed.

## APPENDIX I: QUANTIFERON-TB GOLD TESTING

A QuantiFERON-TB Gold test must be performed **within 1 month** prior to the first administration of study drug.

### Background

The Mantoux tuberculin skin test (CDC, 2000) is the currently accepted, standard method of identifying persons infected with *Mycobacterium tuberculosis*. However, the tuberculin skin test has less specificity due to cross-reactivity with BCG and environmental mycobacteria, and reduced sensitivity, especially in immunocompromised persons (ATS, 2000, Huebner et al, 1993, Jasmer et al, 2002, Shafer and Edlin, 1996). Variability in application and interpretation of the tuberculin skin test is also associated with the inaccuracy of the test (Pouchot et al, 1997). False-positive tuberculin skin test reactions lead to inappropriate treatment with long-term antibiotics, and false-negative tuberculin skin test reactions can result in morbidity and mortality from active TB that could have been prevented. Because of these tuberculin skin test inadequacies, research has focused on new testing methods for detecting TB infection.

The QuantiFERON-TB Gold test is one of the new interferon- $\gamma$  (IFN- $\gamma$ ) based blood assays for TB screening (Cellestis, 2004). It utilizes the recently identified *M. tuberculosis*-specific antigens ESAT-6 and CFP-10 in the standard format, as well as TB7.7(p4) in the In-Tube format, to detect in vitro cell-mediated immune responses in infected individuals. The QuantiFERON-TB Gold assay measures the amount of IFN- $\gamma$  produced by sensitized T-cells when stimulated with the synthetic *M. tuberculosis* specific antigens. In *M. tuberculosis*-infected persons, sensitized T lymphocytes will secrete IFN- $\gamma$  in response to stimulation with the *M. tuberculosis*-specific antigens and, thus, the QuantiFERON-TB Gold test should be positive. Because the antigens used in the test are specific to *M. tuberculosis* and not found in BCG, the test is not confounded by BCG vaccination, unlike the tuberculin skin test. However, there is some crossreactivity with the 3 Mycobacterium species *M. kansasii*, *M. marinum*, and *M. szulgai*. Thus, a positive test could be the result of infection with one of these 3 species of Mycobacterium, in the absence of *M. tuberculosis* infection.

In a study of the QuantiFERON-TB Gold test in subjects with active TB, sensitivity has been shown to be approximately 89% (Mori et al, 2004). Specificity of the test in healthy BCG-vaccinated individuals has been demonstrated to be more than 98%. In contrast, the sensitivity and specificity of tuberculin skin test was noted to be only about 66% and 35% in a study of Japanese patients with active TB and healthy BCG-vaccinated young adults. However, sensitivity and specificity of the tuberculin skin test depends on the population being studied, and the tuberculin skin test performs best in healthy young adults that have not been BCG-vaccinated.

The sensitivity of the tuberculin skin test can decrease significantly in immunocompromised individuals. In asymptomatic HIV-positive persons who developed active TB, the sensitivity of the tuberculin skin test has been reported to be only 40 to 60% (Shafer and Edlin, 1996). There are yet no published studies of the performance of the QuantiFERON-TB Gold assay in immunosuppressed populations, but studies are ongoing and preliminary data suggest that sensitivity is maintained and better than the tuberculin skin test (personal communication, Cellestis). There has been 1 published study using a similar IFN- $\gamma$  based blood test for *M. tuberculosis* infection (T Spot-TB test), which demonstrated a sensitivity of 90% in HIV-positive persons with active TB (Chapman et al, 2002). The ability of the new IFN- $\gamma$ -based tests to detect latent infection has been more difficult to study due to the lack of a gold standard diagnostic test; however, several TB outbreak studies have demonstrated that the new tests correlated better with the degree of exposure that contacts had to the index TB case than the tuberculin skin test (Brock et al, 2004, Ewer et al, 2004).

Although the performance of the new IFN- $\gamma$ -based blood tests for active or latent *M. tuberculosis* infection have not been well-validated in the immunosuppressed population, experts believe these new tests will be at least as sensitive, if not more, and definitely more specific than the tuberculin skin test (Barnes, 2004). For these reasons, this protocol includes the use of the QuantiFERON-TB Gold assay in addition to the tuberculin skin test, the current standard for TB screening, to improve detection of latent TB infection and thereby enhance patient safety.

### Performing the QuantiFERON-TB Gold Test

The QuantiFERON-TB Gold test is available in 2 formats, a standard method and an In-Tube method. The 2 formats differ logically in the manner in which they are performed. In addition, the In-Tube format contains 1 additional *M. tuberculosis*-specific antigen, TB7.7(p4), which is thought to increase the specificity of the test. Results of the QuantiFERON-TB Gold test using either format are acceptable for subjects to enter this trial; however, only the In-Tube format will be provided for this study.

Published studies have only used the QuantiFERON-TB Gold test with the standard method; however, the manufacturing company Cellestis has performed some unpublished studies that demonstrate the comparability of the 2

formats (personal communication, Cellectis). Both formats of the QuantiFERON-TB Gold test are currently approved for commercial use in Europe and certain other countries in which this trial will be conducted. The QuantiFERON-TB Gold test with the standard method was recently approved by the FDA for use in the US. The In-Tube format will be submitted to the FDA for review in the next few years.

To perform the test using the In-Tube format, blood is drawn through standard venipuncture into supplied tubes that already contain the *M. tuberculosis*-specific antigens. Approximately 3 tubes will be needed per patient, each requiring 1 mL of blood. One tube contains the *M. tuberculosis*-specific antigens, while the remaining tubes contain positive and negative control reagents. Thorough mixing of the blood with the antigens is done by shaking the tubes. The blood is then incubated for 16 to 24 hours at 37°C, after which tubes are centrifuged for approximately 5 to 10 minutes at 1500 to 2200 g. Following centrifugation, plasma may be harvested from each tube and placed in aliquot tubes, or the centrifuged tubes themselves may be shipped to the central laboratory at 2°C to 8°C. The central laboratory will perform an enzyme-linked immunosorbent assay (ELISA) to quantify the amount of IFN-γ present in the plasma using spectrophotometry and computer software analysis.

### Interpreting the QuantiFERON-TB Gold Test Results

The central laboratory will analyze and report results for each subject, and study sites will be informed of the results prior to enrolment. Subjects who have a positive QuantiFERON-TB Gold test must receive the same treatment and evaluations for latent TB infection as subjects who have a positive tuberculin skin test to be enrolled in this trial.

### Treatment of Latent Tuberculosis

Local country guidelines for immunocompromised patients should be consulted for acceptable antituberculous treatment regimens for latent TB. If no local guidelines for immunocompromised patients exist, US guidelines must be followed.

The SAP is being amended to update the adverse event section. AE listings and tables for subjects with at least one major protocol deviations related to COVID-19 has been removed due to no infection cases reported.

SAP Version	Approval Date
Original SAP Version 1.0	23 September 2021
Amendment 1 SAP Version 2.0	21 January 2022

ABBREVIATIONS

ACR20	American College of Rheumatology 20% Improvement Criteria
AE	adverse event
ASAS20	Assessment in SpondyloArthritis International Society 20% Improvement Criteria
BASDI	Bath AS Disease Activity Index
BASFI	Bath AS Functional Index
BMI	body mass index
CI	confidence interval
ECG	electrocardiogram
eCRF	electronic case report form
HAQ	Health Assessment Questionnaire
HBV	HBV Hepatitis B Virus
HCV	HCV Hepatitis C Virus
HIV	Human Immunodeficiency Virus
HLA-B27	Human Leukocyte Antigen-B27
ICH	International Conference on Harmonization
ITT	Intention-to-Treat
LOCF	last observation carried forward
MedDRA	Medical Dictionary for Regulatory Activities
NRS	Numerical Rating Scale
PGA	Patient Global Assessment
PsA	Psoriatic Arthritis
RA	Rheumatoid Arthritis
SAE	serious adverse event
SAP	Statistical Analysis Plan
SD	standard deviation
TB	Tuberculosis
TEAE	Treatment-emergent adverse event
VAS	Visual Analogue Scale (Score)

1. INTRODUCTION

This statistical analysis plan (SAP) contains statistical methods for all planned analyses and definitions of analysis population for the study.

1.1. Trial Objectives

1.1.1 Primary Objective

- To assess the safety of subcutaneous (SC) golimumab in patients with active AS or PsA over 24 weeks.

1.1.2 Secondary Objective

- To assess the efficacy of SC golimumab in patients with active AS or PsA as measured by reduction in signs and symptoms of arthritis in active AS or PsA at Week 14.
- To assess achievement of sustained arthritis response in patients with active AS or PsA at Week 24.

1.2. Trial Design

This is an open-label, multicenter, interventional, noncomparative, single-arm, Phase IV study to evaluate safety and efficacy of golimumab (a fully human anti-TNF α mAb, administered subcutaneously) in the treatment of Indian patients with active spondyloarthropathy of AS or PsA. A total of 100 patients will be enrolled in this study. Approximately, 50% patients would be enrolled for each indication-50 patients with active AS, and another 50 with active PsA.

The study consists of three phases- Screening phase (Day -7 to Day -1), Treatment phase (Week 0 to Week 24) and Follow-up phase (Week 25 to Week 32).

Patients will receive golimumab 50 mg SC injections at Week 0 and every 4 weeks thereafter through Week 24. End of treatment (EOT) is defined as the time the last subject completes the week 24 visit. End of study (EOS) visit (in-person or telephonic as per convenience of the patient) will be conducted 8 weeks after the EOT Visit or after the last dose of golimumab (whichever is earlier), to inquire about any AEs experienced by the patient.

A diagram of the study design is provided below in Figure 1.

[figure not shown]

Figure 1: Schematic Overview of the Phase IV clinical study for a single subject

1.3. Statistical Hypotheses for Trial Objectives

No formal hypothesis testing will be tested.

1.4. Sample Size Justification

Approximately 100 patients with spondyloarthropathy (50 patients of AS and 50 patients of PsA) will be enrolled in this Phase IV non-comparative open-label study as per Indian Health Regulatory Authority (DCGI office, n=100) requirement. After enrollment of all 50 participants with one of the disease condition (AS or PsA) the recruitment of participants for that particular disease condition should be stopped, while recruitment for the other disease condition should continue until 50 participants are recruited.

Based on available literature, prevalence rate of AS is approximately 0.25% and prevalence rate of PsA is approximately 0.22% in India. So considering this, close to 50% subjects would be enrolled for each indication.

1.5. Randomization and Blinding

As this is an open and single-arm study, randomization and blinding procedures are not applicable.

2. GENERAL ANALYSIS DEFINITIONS

2.1. Visit Windows

To allow for variation in scheduling, the following set of visit windows (Table 1, Table 2) will be used to assign evaluations to a most appropriate visit for analysis. Furthermore, there will be no gaps between visit windows in order to include as many data points as possible for summarization.

Regardless of the width of the visit window, if more than 1 visit falls in the defined window, the result from the visit closest to the target day will be used. If 2 evaluations are equidistant from the target day, the result from the later visit will be used. Results not included for analysis will be included in the listings.

All assignments will be made in chronological order. Once a visit date is assigned to a visit window, it will no longer be used for a later time point.

Listed below (Table 1, table 2) are the visit windows and the target days for each visit defined in the protocol.

Table 1– Visit Windows for Vital signs and Urine Pregnancy Tests

Scheduled Visit Number	Time Interval (label on output)	Time Interval (Day)*	Target Time Point (Day)
1	Screening	-7 to -1	<= -1
2	Week 0	<= 1	1
3	Week 4	2 to 42	28
4	Week 8	43 to 70	56
5	Week 12	71 to 91	84
6	Week 14	92 to 105	98
7	Week 16	106 to 126	112
8	Week 20	127 to 154	140
9	Week 24	155 to 182	168
10	End of Study	183 to 228	224

Table 2- Visit Window for ASAS20 (BASDAI Evaluation (NRS), BASFI Evaluation (NRS), Total and Night Spinal Pain Assessment (NRS), Patient Global Assessment (NRS)), ACR20

Scheduled Visit Number	Time Interval (label on output)	Time Interval (Day)*	Target Time Point (Day)
1	Screening	-7 to -1	<= -1
2	Week 0	<= 1	1
3	Week 4	2 to 63	28
6	Week 14	64 to 133	98
9	Week 24	134 to 203	168

*Relative to Study Day 1

If subject discontinues the study at any point of time then the visit will be considered as “End of Study” visit.

2.2. Analysis Sets

The analysis sets used in this study are Safety and Intent to Treat (ITT) analysis sets. The efficacy endpoints will be assessed by using ITT analysis set and Efficacy Analysis Set, and safety endpoints by Safety Analysis set.

Safety Analysis Set: The Safety Analysis set includes all subjects who were enrolled and received at least one dose of the study drug.

Intent to Treat (ITT) Analysis Set: The ITT population will include all subjects who were enrolled and received at least one dose of the study drug and have completed Week 24 visit

Efficacy Analysis Set for AS subjects: Efficacy analysis set for AS subjects includes all AS subjects who were enrolled and received at least one dose of the study drug and having at least one non-missing post-baseline ASAS20 score for AS indication.

Efficacy Analysis Set for PsA subjects: Efficacy analysis set for PsA subjects includes all PsA subjects who were enrolled and received at least one dose of the study drug and having at least one non-missing post-baseline ACR20 score for PsA indication.

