#### Statistical analysis:

The safety endpoint of the trial is to demonstrate the safety profile of golimumab in routine clinical practice as assessed by the frequency and proportion of AEs (serious and non-serious AEs) observed during 24 weeks. Efficacy endpoint analyses will include ASAS20 response (for AS patients) or ACR20 response (for PsA patients) at Week 14 and Week 24.

Statistical analysis will be performed separately for each indication.

All statistical analysis will be performed using SAS® software version 9.4 or later. Descriptive statistics will be computed and reported for safety and efficacy variables. A statistical analysis plan will be issued as a separate document providing detailed methods for analysis. For this study, the intent-to-treat population will be analysed. The intention-to-treat population will include all enrolled patients who have received at least 1 study drug administration.

No interim analysis is planned for this study.

| Screening                   | Treatment                            |                                      |                                      |                                       | Assessment                            | Treatment                              |  |  | End of Study                           |
|-----------------------------|--------------------------------------|--------------------------------------|--------------------------------------|---------------------------------------|---------------------------------------|--|--|--|--|
| Day (-7)
(±4 days)       | Week 0
Day 1
(±4 days)         | End of Week 4
Day 28
(±4 days) | End of Week 8
Day 56
(±4 days) | End of Week 12
Day 84
(±4 days) | End of Week 14
Day 98
(±4 days) | End of Week 16
Day 112
(±4 days) | End of Week 20
Day 140
(±4 days) | End of Week 24
Day 168
(±4 days) | End of Week 32
Day 224
(±4 days) |
|                             | Approximately start of Month 1       | Approximately start of Month 2       | Approximately start of Month 3       | Approximately start of Month 4        |                                       | Approximately start of Month 5         | Approximately start of Month 6         | Approximately end of Month 6           | Approximately end of Month 8           |

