## **11. STATISTICAL METHODS**

Statistical analysis will be done by the sponsor or under the authority of the sponsor. A general description of the statistical methods to be used to analyse the safety and efficacy data is outlined below. Specific details will be provided in the Statistical Analysis Plan.

Statistical Analysis Plan will be issued as a separate document, providing detailed methods for analysis planned in the study. All statistical analysis will be performed using SAS® software version 9.4 or later. For study endpoints analysis, intention-to-treat (ITT) population will be considered.

Continuous data variables will be summarized using descriptive statistics (number of subjects, mean, standard deviation [SD], median, minimum and maximum). Change from baseline will be calculated where appropriate. Subject-wise data listing will be provided. All categorical data will be summarized using frequency counts and percentages. Statistical analysis will be performed separately for each indication.

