**11.1.2. Intent-to-Treat Population**

The ITT population will include all subjects who were enrolled and received at least one dose of a study drug and have completed Week 24 visit.

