4.1.2. Analysis Methods

Intent-to-treat population will be used for efficacy endpoints. Analysis for efficacy endpoints will be repeated on the efficacy analysis set.

The ASAS20 and ACR20 response evaluations will be performed on week 0, week 4, week 14 and week 24. The scores obtained from the respective domains will decide the responder for

ASAS20 or ACR20 criteria. Proportion of patients who achieve ASAS20 or ACR20 criteria at week 24 will be calculated, along with a 95% confidence interval.

For ASAS20, if data for percent improvement from baseline is missing at a particular assessment visit, then the response for the subject at that visit will be considered as missing.

If a subject's baseline value is zero (i.e. for ACR no disease activity for one assessment,) or missing, the subject should be considered as non-responder.

If all its components for a composite endpoint (i.e. score for subdomain as captured in CRF) are missing, the response for the endpoint at the particular visit will be set as missing; if not all its components are missing, LOCF will be used to impute the missing components and the value of the composite endpoint will be derived based on the imputed components.

If subject discontinues due to lack of efficacy, subject should be considered as non-responder.

If there is an Increase in the dose of MTX subject should be considered as non-responder.

The analysis will be done separately for each indication.

The scores for individual domains for both the ASAS20 and ACR20 will be descriptively summarized at all analysis visits.

The individual domain scores will be listed for each criteria.

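### The ITT set is limited to patients who completed Week 24, which contradicts the synopsis and makes even the Week 14 ITT result depend on later attendance

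*SAP*

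**What the plan says.** The current documents hold two definitions of the ITT population.

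- Protocol synopsis, Statistical analysis: "The intention-to-treat population will include all enrolled patients who have received at least 1 study drug administration".
- Protocol 11.1.2 limits the set to enrolled subjects who "received at least one dose of a study drug and have completed Week 24 visit".
- SAP 2.2 repeats that limit: "all subjects who were enrolled and received at least one dose of the study drug and have completed Week 24 visit".

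The protocol names no other efficacy population. Its Section 11 states: "For study endpoints analysis, intention-to-treat (ITT) population will be considered". SAP 4.1.2 says "Intent-to-treat population will be used for efficacy endpoints" and then "Analysis for efficacy endpoints will be repeated on the efficacy analysis set". The Efficacy Analysis Set, defined only in SAP 2.2, asks for one dose and at least one post-baseline ASAS20 or ACR20 result, with no Week 24 condition. The endpoints in SAP 4.1 are ASAS20 (AS) and ACR20 (PsA), each at Week 14 and Week 24. The Safety set is everyone enrolled and dosed.

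**The concern.** The label ITT tells a reader that every treated patient is counted. With the Week 24 condition it is a completers set under that label. Three consequences follow.

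- Entry to the Week 14 ITT analysis depends on something that happens 10 weeks later.
- The condition works against other rules in the plan. SAP 4.1.2 says "If subject discontinues due to lack of efficacy, subject should be considered as non-responder", yet such a patient can be removed before being counted as a failure. Protocol 10.1 says that the last assessment of those who stop treatment early is to be analysed, yet the condition can exclude them.
- If patients who leave respond less often than those who stay, the reported response is too high.

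Neither document defines what completing the Week 24 visit means, so two programmers could build different sets from the same data.

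**Working it through.** **No planned figure to reproduce.** The sample size (50 AS + 50 PsA = 100) is set by the regulator, and no drop-out rate, response rate or power is stated. The check therefore has two parts: who is removed, and what that could do to the proportions.

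**Who is removed.** The phrase can be read in three ways.

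1. *The scheduled visit (Day 168 ± 4) was attended.* Everyone who leaves earlier is removed. A patient who stops treatment but stays in follow-up, as Protocol 10.2 allows, can still attend and be kept.
2. *An efficacy evaluation falls in the Week 24 window of SAP Table 2 (Day 134 to 203).* With a ±4-day visit window, an early end-of-treatment (EOT) evaluation maps as follows:
   - Week 8 (Day 52–60) falls in the Week 4 window (2–63).
   - Week 12 (80–88) and Week 16 (108–116) fall in the Week 14 window (64–133).
   - Week 20 (136–144) falls in the Week 24 window and is kept.

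   SAP 2.1 closes off reuse of a date: "Once a visit date is assigned to a visit window, it will no longer be used for a later time point". SAP Table 1, for vital signs and pregnancy tests, gives a different Week 24 window (Day 155–182), and Week 20 falls outside that one.
3. *Any early EOT visit counts.* The EOT definition and Protocol 10.2 and 10.3 may allow this. Only patients with no EOT or Week 24 visit are then removed. Against this, SAP 2.1 relabels a study discontinuer's visit as End of Study, which also weakens reading 2 for such patients.

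On all three readings, a patient seen at Week 14 and then lost with no EOT visit is removed from the Week 14 ITT result.

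**What it could do.** All rates here are assumptions: 50 dosed per indication, 70% response among those kept, r removed, and response p among those removed.

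Proportion over all 50 = [(50 − r) × 0.70 + r × p] / 50, so gap = 0.70 − that = (r/50) × (0.70 − p).

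*Week 14, condition alone, all removed patients having an observed Week 14 result:*

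| r | p = 0.70 | p = 0.50 | p = 0.30 |
|---|---|---|---|
| 5 | 0.10 × 0 = 0 | 0.10 × 0.20 = 2 points | 0.10 × 0.40 = 4 points |
| 10 | 0.20 × 0 = 0 | 0.20 × 0.20 = 4 points | 0.20 × 0.40 = 8 points |

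For p above 0.70 the sign reverses.

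*Week 24, condition alone:* 10 leavers have no Week 24 data, k of them left for lack of efficacy (non-responders), and other missing responses stay out of the denominator. The proportion is 28/(40 + k), with exact (Clopper-Pearson) 95% intervals.

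| k | Proportion | 95% CI | Gap from 28/40 |
|---|---|---|---|
| 0 | 28/40 = 70.0% | 53.5–83.4% | 0 |
| 2 | 28/42 = 66.7% | 50.5–80.4% | 3.3 points |
| 5 | 28/45 = 62.2% | 46.5–76.2% | 7.8 points |

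*Week 24, all leavers in the denominator:* with p = 0, 0.50 and 0.70, the gap is 7, 2 and 0 points for r = 5, and 14, 4 and 0 points for r = 10. The 14-point case is 28/50 = 56.0% (41.3–70.0%) against 70.0%. The p = 0 results need a second rule, that missing counts as non-response, unless every leaver left for lack of efficacy. If Protocol 10.1 is applied, p is the response at the leavers' last assessment.

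*Reading 3:* with, for example, 2 patients lacking any EOT visit, the gap is at most (2/50) × 0.70 = 2.8 points.

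**The case against.** The strongest reply is the planned repeat on the Efficacy Analysis Set. Any patient with an observed Week 14 response is in that set by definition, so every patient in the Week 14 illustration is recovered there, and only the ITT versions of the results depend on Week 24 attendance. This stands as substantial mitigation for Week 14. It does not resolve the two ITT definitions, and the figure labelled ITT stays a completers figure. The repeat set is absent from the protocol, and because it needs a post-baseline score it is not the synopsis ITT either.

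Other points carry some weight:

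- SAP 4.1.2 specifies the calculated proportion and confidence interval only for Week 24. Week 14 comes in through the endpoint list and the general sentence assigning efficacy to ITT.
- The protocol body and the SAP agree, and the synopsis is the outlier, with nothing to say which governs. Renaming the set as completers would also cure the misleading label, but would leave the protocol with no efficacy set of all treated patients.
- The largest gaps, 7 and 14 points, are not effects of the condition alone unless all leavers left for lack of efficacy.
- Efficacy is secondary and descriptive, with no hypothesis test.

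**Conclusion.** The concern holds. The current documents define ITT in two incompatible ways unless every dosed patient completes Week 24, and the version in Protocol 11.1.2 and SAP 2.2 selects patients on later attendance. The documents do not allow the size to be estimated. On the assumed rates, the condition alone shifts the Week 14 result by 0 to 8 points and the Week 24 result by 0 to 7.8 points, or 14 points if all 10 leavers left for lack of efficacy. The shift is upward only if leavers respond less often than those who stay; it is nil if they respond alike and reversed if they respond more often. This should be fixed, but it does not threaten the trial's main purpose: the primary safety analysis uses the Safety set, and a broader efficacy repeat is already planned.

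**What to change.** 1. Delete the Week 24 condition from Protocol 11.1.2 and SAP 2.2, so that ITT matches the synopsis at both time points. ITT then has the same members as the Safety set, and this should be stated.
2. Keep the lack-of-efficacy and last-observation-carried-forward (LOCF) rules within that set. State in SAP 4.1.2 whether patients with a missing response stay in the denominator, and reconcile this with Protocol 10.1. If dosed patients with no usable data at a visit are to count as non-responders, amend the missing-data text in Protocol 11, SAP 2.6 and SAP 4.1.2, because the SAP sections now leave an all-missing visit missing and the protocol plans no imputation beyond LOCF.
3. Keep Week 24 completers only as a labelled sensitivity set. Say there whether an early EOT visit, or an evaluation on Day 134 to 203, counts as the Week 24 visit.

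The cost is a SAP amendment and a formal protocol amendment with IEC/IRB approval (Protocol 17.1). No new data are needed. SAP version 2.0 (21 January 2022) was itself amended because no COVID-19 infection cases had been reported, which suggests that some data were already known. The change should therefore be disclosed as late, with results on both sets shown. Reported response rates may fall, but the documents do not show that they will.
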